## 9.5 Monitoring

Implementation of this study will be monitored at multiple levels, consistent with standard IMPAACT procedures. A Study Progress, Data, and Safety Monitoring Plan (SPDSMP) that details monitoring roles and responsibilities and data to be reviewed at each level will be prepared before the study opens to accrual. Sections 11 and 12 provide more information on on-site monitoring and quality management at the site level. Further information on monitoring of study progress, quality of study conduct, and participant safety across sites is provided below.

## 9.5.1 Dose-Finding Phase

During the dose-finding phase of the study, the CMC will review study data, or data from other ongoing studies of the study drugs in pediatric populations, with the aim of determining the proposed dose, per weight band, while protecting participant safety and as further described in this section.

At a minimum, the PK and safety data will be reviewed during routine monitoring for both cohorts as follows:

- (i) Safety data will be reviewed approximately monthly, and the CMC will take action as needed according to the guidelines described in Section 9.5.3 and
- (ii) PK data will be reviewed as soon as results become available according to specifications in Section 10.

In addition to the routine monitoring of PK and safety data, there will be two Cohort 1 interim analyses, please refer to Section 3. All available PK, safety, viral load, tolerability, and other relevant data will be reviewed by the CMC, and the Safety Guidelines (Section 9.5.2) will be assessed based on safety data through Week 12. These interim analyses, and/or ongoing reviews of relevant data within the study or from other ongoing studies of the study drugs in pediatric populations, will determine whether any modifications should be made to the weight band dosing, including whether to continue on every 4 weeks(Q4W) or to switch to every 8 weeks(Q8W) for the CAB and RPV injectable. If the Protocol Team determines that a dose modification is needed, accrual will be paused and the SMC will be notified as described in Section 9.5.4.

## 9.5.2 Safety Guidelines

The Safety Guidelines will consider the adverse event severity, seriousness and attribution to the study drugs. Adverse event attribution to the study drugs will be based on site assessment.

The Safety Guidelines are considered not met, i.e., dose has failed the Safety Guidelines, if:

- at least one participant experienced an adverse event that is fatal or life-threatening and is assessed as related to study drug(s); or
- more than 25% of the participants (e.g., 3 or more of 8 dose-evaluable participants in an interim analysis) experience a Grade 3 or higher adverse event (excluding injection site adverse events, e.g., ISRs) assessed as related to study drug(s) or experience any adverse event assessed as related to study drug(s) that results in permanent discontinuation of the study drug(s).

If none of these conditions are met, then the dose being evaluated has passed the Safety Guidelines.

Given the small sample sizes in a Cohort 1 interim analysis, the information available for safety decisions based on the Safety Guidelines may be imperfect. Two types of sampling errors are possible: 1) if the true rate of toxicity is too high to warrant exposure to the current dose of study drug, the sample data may pass the Safety Guidelines and 2) if the true rate of toxicity is low enough that further exposure to the current dose is warranted, the sample data may fail the Safety Guidelines.

The extent to which the Safety Guidelines protect against the errors described above can be assessed by examining various hypothetical rates of "true toxicity" which could occur if the study drug were used extensively among the participant population at the dose level under question. The hypothetical situations presented in Table 9. (i.e., interim analysis assessment of the Safety Guidelines) range from conditions under which a given dose level would cause a high incidence of severe and life-threatening adverse events to conditions under which severe adverse events would be relatively rare and would not be life-threatening.

Table 9 uses a multinomial response model to assess the probability of failing the Safety Guidelines under each of these hypothetical situations. The calculations are performed as follows: Each of the eight participants represents a trial, which may have 1 of 3 mutually exclusive outcomes: (i) death or life-threatening adverse event assessed as related to study drug; (ii) a Grade 3 or 4 non-life-threatening adverse event assessed as related to study drug; and (iii) a relatively benign outcome, satisfying neither the criteria in (i) nor (ii).

Table 9.

Probability of Eight Dose-Evaluable Participants Failing Safety Guidelines Under Potential Rates of True Toxicity

True Tox		
Grade 3 or 4 Non-Life Threatening Drug-Related AE	Life Threatening or Fatal Drug- Related AE	Probability of Failing Safety Guidelines
0.50	0.00	0.86
0.50	0.05	0.93
0.50	0.25	1.00
0.25	0.00	0.32
0.25	0.05	0.57
0.25	0.25	0.95
0.05	0.00	0.01
0.05	0.05	0.34
0.05	0.25	0.90
0.00	0.05	0.34
0.00	0.25	0.90

For each of the hypothetical situations above, it is assumed that a sample of eight participants is drawn from the population and that the Safety Guidelines, summarized above, are followed. The probability of failing the Safety Guidelines represents the sum of the probabilities of these sets of results, and "1 minus the probability of failing the Safety Guidelines" represents the probability of passing the guidelines. The "True Toxicity Rates" presented in the table, along with the true rate of having neither of the two types of adverse events represented by the true toxicity rates (which is "1 minus the sum of the true toxicity rates"), provide the probabilities for the outcomes that are used in the multinomial calculations for each of the hypothetical situations.

As an example of how to read Table 9, the second row shows that there is a 93% chance of failing the Safety Guidelines at doses in which the true rate of drug related life-threatening adverse events is 5% and the true rate of drug-related non-life-threatening adverse events is 50%. Under the conditions specified in row 2 of the table, assuming that further exposure to a dose that has these true rates of adverse events would be undesirable, the 7% chance of NOT failing the Safety Guidelines would represent the probability of error. As a further example, the table also shows that there is 1% chance of failing when the true rate of a drug-related Grade 3 or 4 non-life-threatening adverse event is only 5% and the true rate of drug-related life-threatening or fatal adverse event is zero. Assuming that the potential benefits associated with further exposure to this dose would outweigh the risks associated with this relatively low rate of toxicity, failing the Safety Guidelines under these conditions would be an error.

## 9.5.3 Monitoring by the Protocol Team

#### Study Progress and Quality of Study Conduct

The Protocol Team is responsible for continuous monitoring of study progress, including timely achievement of key milestones, and quality of study conduct.

The Protocol Team will monitor participant accrual based on accrual reports that will be generated approximately monthly by the IMPAACT Statistical and Data Management Center (SDMC) as well as site activation. The team will monitor the timing of site-specific study activation, which will determine when each site will begin accruing participants, and actual accrual following activation. The team will monitor site actual accrual relative to site-specific accrual projections. Accrual performance will be reported by the DMC, by site and across sites, and the team will review study progress approximately monthly.

The CMC will determine the dose-evaluability and evaluability status of participants, based on definitions in Section 3.2, and the SDMC will record CMC determinations in the database. Relevant study treatment information and weight band at entry of the participant will be provided to the CMC to facilitate assessment of a participant's dose-evaluability and evaluability status in Cohort 1. For both cohorts, the team will monitor and manage accrual such that fulfillment of the sample size targets specified in Section 3 are achieved. The team will communicate to sites when accrual must be managed and when sample size targets are reached.

The Protocol Team will also monitor participant retention and adherence to study product regimens. On behalf of the Protocol Team, the CMC will monitor other key indicators of the quality of study conduct (e.g., protocol deviations, adherence to the study product regimens, data quality, and data and specimen completeness) based on reports generated by the SDMC and take action with study sites as needed to ensure high quality study conduct throughout the period of study implementation.

## Participant Safety

On behalf of the Protocol Team, the CMC will closely monitor participant safety through routine review of safety data reports generated by the SDMC. These reports will be based on the safety-related data collection described in Section 7.2 and will provide listings and/or tabulations of adverse events and laboratory test results. The CMC will review these reports approximately monthly. At the time of each review, the DAIDS Medical Officer will also review any EAEs reported to the DAIDS Safety Office that are not yet reflected in the data reports.

The CMC will continually evaluate the pattern and frequency of reported adverse events and assess for any individual occurrences or trends of concern. The CMC will also monitor for the occurrence of adverse events meeting criteria to convene an *ad hoc* SMC review, as described in Section 9.5.4.

The CMC may discuss the reporting of any adverse event and assessment of relationship to study drug(s) with the site investigator. For adverse events that may trigger an *ad hoc* SMC review specified in Section 9.5.4, the CMC may provide an assessment of adverse event attribution to the study drug(s).

## 9.5.4 Monitoring by the SMC

An independent IMPAACT Study Monitoring Committee (SMC) will review this study regularly, following policies described in the IMPAACT Manual of Procedures.

The SMC will monitor study progress, quality of study conduct, and participant safety. SMC reviews will occur at least annually and on a more frequent or *ad hoc* basis if any issues or concerns arise. Additionally, an SMC review will occur prior to the CMC finalizing any dosing regimen modifications, as described in Sections 3.2 and 5.1.2, including a modification from Q4W to Q8W injection dosing. *Ad hoc* SMC reviews may occur as indicated below (*Participant Safety*).

Based on any of its reviews, the SMC may recommend that the study proceed as currently designed, proceed with design modifications, or be discontinued. The SMC may also provide operational recommendations to help address any study implementation challenges that may be identified during their reviews.

#### Study Progress and Quality of Study Conduct

The SMC will generally review the same types of study progress and quality of study conduct data reports as the Protocol Team and CMC.

## Participant Safety

Routine SMC reviews, as described above, will include a review of safety reports, as described in the SPDSPM. In addition, *ad hoc* SMC reviews may be triggered based on the criteria described below from routine monitoring (see Section 9.5.3) or from the interim analyses (see Section 9.5.1) conducted by the CMC. For these *ad hoc* SMC reviews, reports provided to the CMC and relevant to the trigger for the *ad hoc* SMC review will be provided to the SMC. SMC reviews may also include review of additional data, if requested by the CMC.

*Ad hoc* SMC reviews will occur in the following scenarios:

- 1. In the event of **any fatal or life-threatening adverse event**, the CMC will review the event as soon as possible:
  - If the site investigator assesses the adverse event as related to study drug(s), participant accrual will immediately be paused and an SMC review will be convened as soon as possible. The CMC may choose to pause administration of study drug(s) pending the outcome of the SMC review.
  - If the site investigator assesses the adverse event as not related to study drug(s), participant accrual and administration of study drug(s) will continue. The SMC will be informed of the adverse event.
- 2. In the event that three or more of the dose-evaluable participants in a planned interim analysis experience a Grade 3 or higher adverse event (excluding injection site adverse events, e.g. ISRs) assessed by the site investigator as related to study drug(s) or experience any adverse event assessed by the site investigator as related to study drug(s) that results in permanent discontinuation of study drug(s) prior to accruing the eight dose-evaluable participants targeted for the interim analysis, participant accrual will immediately be paused and an SMC review will be convened as soon as possible. The CMC may choose to pause administration of the study drug(s) in the cohort pending the outcome of the SMC review.
- 3. In the event the CMC identifies any concerns based on review of PK, safety, viral load, tolerability, or other relevant data, an SMC review will be convened. The CMC may choose to pause participant accrual and/or administration of study drug(s) pending the outcome of the SMC review.
- 4. In the event the CMC recommends a dosing regimen modification, an SMC review will be convened. The CMC will pause participant accrual of the relevant weight band(s) and may pause administration of study drug(s), pending the outcome of the SMC review.

# 9.6 Analyses

This section provides a brief summary of the planned statistical analyses for outcome measures in Section 9.2. Details will be specified in a separate, comprehensive Primary SAP.

Separate analysis will be done for Cohorts 1, 2a and 2b.

For the main analyses, safety outcome measures including adverse event attribution to the study drug(s) will be done using site assessments. Sensitivity analyses will also be performed for these safety outcome measures but using CMC assessments; the CMC will provide an assessment of attribution to the study drug(s) for adverse events that may potentially be classified as a drug-related safety failure event in the sensitivity analyses.

#### Baseline:

The **baseline value** will be the latest assessment with a non-missing value prior to the first study drug exposure.

#### *Oral bridging:*

Oral bridging will be considered as a part of permitted treatment but will not be counted as a substitute for an injection. Occurrence of oral bridging will be summarized and details will be provided in the Primary SAP.

Supplementary analysis for Cohort 2a: Analyses based on pooled Cohort 1 and 2a data
Participants in Cohort 1 and 2a would have been assigned or opted to receive CAB + RPV oral leadin followed by CAB + RPV injectable. The main analysis for Cohort 2a will be on Cohort 2a data
only, but as an additional analysis; the same analysis may be done on pooled Cohort 1 and Cohort 2a
data, as appropriate.

#### Analysis of Safety and Tolerability Data:

The population of interest for the safety and tolerability analyses are virologically suppressed children living with HIV, two to less than 12 years of age, who received oral CAB + RPV (oral and injectable). Other analysis populations of interest, e.g., children on recommended dose population, may be added and specifications will be included in the Primary SAP.

Separate analyses will be done for each of the safety outcome measures. In addition to the analyses of the safety outcome measures, the proportion of participants who have injection site adverse events, adverse events related to study procedure (e.g., injection site reactions), and any grade adverse event related to the study drug(s) will be provided.

Summaries of worst grade adverse events by MedDRA Preferred Term (PT) grouped by System Organ Class SOC will be generated for: (i) all adverse events, and (ii) all adverse events assessed by site as related to the study drug(s).

Cohorts 1 and 2 analysis groups will be based on weight at entry (i.e., pooled data across Weight Bands 1 and 2; and pooled data across Weight Bands 3, 4 and 5) and study drug dose for the oral lead-in and/or at start of the injectable phase. The main safety analysis will include estimates overall and per analysis group. As additional analysis, per weight band estimates will be provided recognizing that due to small sample size these estimates will be less precise.

Analysis of Virology, Immunology, Phenotypic and Genotypic Resistance Data: The population of interest for the analyses of virology and immunology data are virologically suppressed children living with HIV, 2 to less than 12 years of age, who received oral CAB + RPV (oral and injectable).

The population of interest for the analysis of phenotypic and genotypic resistance data are the virologically suppressed children living with HIV, 2 to less than 12 years of age, who received oral CAB + RPV (oral and injectable) and are confirmed virologic failure while on CAB + RPV. Cohort 1 and 2 analysis groups will be based on study drug dose for the oral lead-in and/or at start of the injectable phase.

#### Analysis Sets:

Analysis Set	Descriptions
Screened	All who were screened for study eligibility
Enrolled	All who pass the study entry eligibility criteria and enrolled to
	the study
All Treated	All study participants who received at least one dose of the
	study drug.
	TO A 11 TO ( 1 1 1 1 1 1 1 1 1 1 1 1 1 1 1 1 1 1
	The All Treated population will be used for the safety,
	tolerability, acceptability, virology and immunology analyses.
Confirmed Virologic	All study participants in the All Treated analysis set who meet
Failure	the criteria of confirmed virologic failure
	The Confirmed Virologic Failure' population will be used for
	the resistance analyses
Pharmacokinetic	All study participants in the All Treated analysis set with at
(PK)	least one non-missing PK assessment.
	Note: PK data will be reviewed by the study team to determine
	whether or not the sample will be excluded from the PK
	analyses.

Additional analyses sets may be added and will be described in the Primary SAP.

### 9.6.1 Primary Safety Analyses

#### 9.6.1.1 Cohort 1: Oral lead-in safety

The analyses will focus on safety of the CAB and RPV oral lead-in while on treatment based on Cohort 1 data.

Overall and per group point and 95% Clopper-Pearson CI estimates of the proportion of children who (i) experience at least one drug-related safety failure event, (ii) experience at least one grade 3 or higher adverse event, (iii) experience at least one SAE, and (iv) prematurely permanently discontinue study treatment due to an AE, during the oral lead-in phase will be generated.

- For (i): Point estimates of the proportion of children who experience each of the drug-related safety failure events will be provided.
- For (ii): Point estimates of the proportion of children who (a) experience at least one grade 3 or 4 adverse event, (b) experience a grade 5 adverse event, will be provided.

## 9.6.1.2 Cohort 1: Safety of 24 weeks of CAB + RPV (oral and injectable)

The analyses will focus on safety of the CAB + RPV (oral and injectable) through Week 24 while on treatment.

Overall and per group point and 95% Clopper-Pearson CI estimates of the proportion of children who (i) experience at least one drug-related safety failure event, (ii) experience at least one grade 3 or higher adverse event, (iii) experience at least one SAE, and (iv) prematurely permanently discontinue study treatment due to an adverse event, through Week 24 will be generated.

- For (i): Point estimates of the proportion of children who experience each of the drug-related safety failure events will be provided.
- For (ii): Point estimates of the proportion of children who (a) experience at least one grade 3 or 4 adverse event, (b) experience a grade 5 adverse event, will be provided.

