#### 1.3 Rationale

IMPAACT 2036 is a Phase I/II study to propose the weight-band dosing of oral cabotegravir (CAB) + oral rilpivirine (RPV) followed by long-acting injectable CAB (CAB LA) + long-acting injectable RPV (RPV LA) and assess the long-acting injectable regimen with and without an oral lead-in period in virologically suppressed children living with HIV-1, two to less than 12 years of age and weighing ≥10 kg and <40 kg. Both the European Medicines Authority (EMA) and United States Food and Drug Administration (FDA) have determined that the CAB LA + RPV LA regimen would not provide a significant therapeutic benefit over existing therapies in children less than two years of age and they will, therefore, not be included in the study population for IMPAACT 2036.

# 1.3.1 Rationale for the oral lead-in prior to injectable dosing in Cohort 1

The CAB LA and RPV LA formulations provide prolonged drug exposures, resulting from gradual release from the IM injection, that exposes the injected individual to detectable levels of cabotegravir and rilpivirine for up to 52 weeks or longer after an injection. An oral lead-in period of daily oral CAB and RPV prior to injectable administration, with serial safety assessments, can allow identification of any acute toxicity prior to administration of a non-dialysable, non-removable depot injection. A similar oral lead-in period was initially employed in previous trials in adults using these LA formulations. Throughout the course of the clinical development program for CAB LA and RPV LA, including the large Phase 3/3b trials FLAIR, ATLAS and ATLAS-2M, an oral lead-in phase of cabotegravir (30 mg) along with rilpivirine (25mg), administered daily for 30 days, was an integral component of these trials and allowed for a safety assessment before study participants were allowed to advance to the LA phase of these studies. As a result, all study participants underwent a one-month period of oral dosing with CAB/RPV followed by an evaluation of safety labs, and if labs were within normal limits, participants were allowed to transition into LA dosing. PK and safety data are necessary with the oral dosing to support labeling of an appropriate oral dose for children.

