#### 9.2 Outcome Measures and Estimands

The primary and secondary outcome measures listed in this section will be further described in the study's Primary SAP, which will define the contents of the final analysis reports.

The Safety Outcome Measures will consider the adverse event's severity (i.e., grade), seriousness (i.e., using ICH criteria for serious events), and attribution to the study drugs. The following specifications will also be used for the safety outcome measures and are referenced in Table 4:

- **Drug-related safety failure events** include the following:
  - o Grade 3 or higher adverse events assessed as related to study drug(s)
  - SAEs assessed as related to study drug(s)
  - Premature permanent discontinuation of study drug(s) due to an adverse event assessed as related to study drug(s)
- Adverse event attribution to the study drugs will be based on site's assessment.
- **HIV-1 Virologic Outcome Measures** based on HIV-1 RNA (copies/mL), will be calculated according to the US FDA-defined Snapshot Algorithm and will use 50 and 200 copies/mL as threshold with three main categories each.
  - o HIV-1 RNA <50 copies/mL, HIV-1 RNA ≥50 copies/mL, and no virologic data.
  - o HIV-1 RNA <200 copies/mL, HIV-1 RNA ≥200 copies/mL, and no virologic data.
- Confirmed virologic failure is defined in Section 8.3.

The primary objectives for Cohort 1 will be supported by the PK outcome measures and safety described in Section 10.2 and in the table below, respectively. As stated above, the PK-related study objectives will be supported by the PK outcome measures and planned analyses as described in Section 10.

Table 4.
Outcome Measures

	Outcome Measures	
9.2.1 Coho	rt 1 Primary Outcome Measures	
9.2.1.1	Safety of the CAB + RPV oral lead-in and 24 weeks of CAB + RPV (oral and injectable)	
	
 
Proportion of children who experience the following during the CAB + RPV oral lead-in period:         
 
drug-related safety failure event
 
grade 3 or higher adverse event
 
SAE
 
premature permanent discontinuation study treatment due to an adverse event
 
 
 
	
	
 
Proportion of children who experience the following during the 24 weeks of CAB + RPV (oral and injectable):         
 
drug-related safety failure event
 
grade 3 or higher adverse event
 
SAE
 
premature permanent discontinuation study treatment due to an adverse event
 
 
 
	

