condition	through Week 4 (see Schema on	through Week 4, followed by LA		
	treatment details)	CAB + LA RPV Q4W or Q8W		
		through Week 24 (see Schema on		
Intercurrent	Duama atuma na mma an ant	treatment details)		
events (ICE)	Premature permanent discontinuation of study drugs for	Premature permanent discontinuation of study drugs for		
events (ICE)	any reasons through week 4 has	any reasons through Week 24 has		
	impact on safety assessment.	impact on safety assessment. While-		
	While-on-treatment strategy will	on-treatment strategy will be applied		
	be applied to address this ICE.	to address this ICE.		
	Other analysis approaches may also be explored to address missing			
	values due to premature permanent discontinuation as a part of sensitivity			
	analysis. Details will be described in the Statistical Analysis Plan (SAP).			
Population-	Proportions of children experiencing the safety outcome measures and			
level summary	their two-sided 95% confidence interval			

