# 9.4 Sample Size and Accrual

Up to 90 children will be enrolled across Cohorts 1 and 2. Cohort 1 will enroll up to 70 participants in order to achieve at least 50 evaluable participants. Cohort 2 will open to accrual once accrual to Cohort 1 is complete and results on Week 12 interim analyses are available. Additional specifications on weight-band accrual targets (both per weight band and across weight bands) are specified in Section 3.1. Sample size specifications of parents/caregivers of child participants for the behavioral assessments and qualitative in-depth interviews to assess study drug acceptability and tolerability are in Sections 3.1 and 3.4. The sample size requirements are primarily driven by consideration for main analyses for the safety study objectives. For example, for the 50 participants included in Cohort 1 primary safety analysis, if 2 (4%) experience a safety failure event as defined in Section 9.2, the 95% Clopper-Pearson Confidence Interval would be 0-14% (please see Table 6), which provides sufficient precision to exclude a rate ≥ 15% based on the upper limit of CI. Moreover, of the 50 Cohort 1 participants included in the primary safety analysis, the probability of observing at least one participant who experiences such an event is high (87%). assuming a true rate of the safety failure event in the study population of 4% (please see Table 8).

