## 9.6.3 Other Analyses

Long-term washout safety of CAB LA and RPV LA through 48 weeks following permanent treatment discontinuation

Overall and per group point and 95% Clopper-Pearson CI estimates of the proportion of children who: (i) experience at least one drug-related safety failure event, (ii) experience at least one grade 3 or higher adverse event, and (ii) experience at least one SAE through 48 weeks following permanent discontinuation of CAB LA + RPV LA.

Regulatory Submission

For regulatory submission purposes, the analyses will follow specifications in the Primary SAP. Additional analyses/reports and additional analyses specifications for regulatory submission tables, figures, and listings will be specified in a separate document.

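### In injected children, a first Grade 3+ AE or SAE that starts after permanent discontinuation but by Week 24 is left out of the Week 24 safety proportions; a supplementary estimate would show it cheaply (low priority)

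*Protocol*

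**What the plan says.** Section 9.6.1.2 sets the scope of the Week 24 safety analysis: "The analyses will focus on safety of the CAB + RPV (oral and injectable) through Week 24 while on treatment". It estimates four proportions: (i) any drug-related safety failure event, (ii) any Grade 3 or higher adverse event, (iii) any SAE, and (iv) permanent discontinuation due to an adverse event.

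Table 5 in 9.2 lists permanent discontinuation for any reason as the intercurrent event, to which a while-"on-treatment strategy will be applied". It adds "Other analysis approaches may also be explored to address missing" values, as sensitivity analysis, with details left to the SAP.

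In the Analysis Sets table of 9.6, "The All Treated population will be used for the safety" analyses, among others. All Treated means at least one dose received.

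The composite in (i) includes "Premature permanent discontinuation of study drug(s) due to an adverse event assessed as related to study drug(s").

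Sections 9.6.2.1 and 9.6.2.2 carry the same restriction to Weeks 48 and 72 (Week 44 in Cohort 2b). Section 9.6.3 has a separate washout analysis of outcomes (i) to (iii), the last being the proportion who "experience at least one SAE through 48 weeks following permanent discontinuation of CAB LA + RPV LA".

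On exposure, 1.3.1 explains the oral lead-in as a check before "administration of a non-dialysable, non-removable depot injection". Section 1.2.1 reports CAB in plasma for up to 52 weeks or longer, and 1.2.2 gives RPV LA an apparent half-life of 200 days in adults.

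**The concern.** For an oral drug, ending the count at discontinuation roughly matches the end of exposure. For this product it does not. A child last injected at Week 12 who has a first SAE at Week 18 has it with both drugs still present. The child remains in the denominator, but the event does not enter the Week 24 numerator.

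The outcomes are affected differently:

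- (ii) and (iii) lose any first qualifying event that starts after stopping and by Week 24.
- (i) loses it only when the child stopped for a reason other than a related adverse event, because a related-event discontinuation already counts.
- (iv) is not affected.

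The effect on the Week 24 proportions is downward or nil, never upward. What is at stake is how fully the headline figure describes 24-week safety of a depot regimen in children. The data needed are already planned: injected children who stop enter the 48-week LSFU schedule (6.6), and adverse events are reviewed at each of its visits (6.6.1, 6.6.2).

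The point is limited to injected children. A child who stops during the oral lead-in has no depot and, pregnancy apart, leaves the study about 28 days after the last oral dose (8.5).

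**Working it through.** **The plan's own figures (9.4).** For 2 failures in 50, the exact Clopper-Pearson 95% interval is 0.5% to 13.7%, which matches the stated 0-14%. The chance of at least one failure in 50 at a true rate of 4% is 1 − 0.96^50 = 0.870, matching the stated 87%.

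**Inputs for the size of the gap.** The protocol gives no paediatric rate for either quantity, so both are assumed over a range:

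- R, the true 24-week risk of a first event: 5%, 10%, 20%.
- d, the share stopping between Weeks 4 and 24: 5%, 10%, 20%. For context, 1.2.5 reports 4% adult discontinuation for adverse events, and 1.2.4 reports 2 of 23 adolescents (8.7%).

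Further assumptions: a constant event hazard that is the same before and after stopping; a constant stopping rate, independent of event risk; and an on-treatment period that ends at discontinuation.

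**Formula.** Per week, h = −ln(1 − R)/24 and g = −ln(1 − d)/20. The uncounted share U is the chance of stopping at week s (4 to 24) with no event so far and then having a first event by Week 24. Integrating over s:

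U = e^(−4h) × g/(g+h) × [1 − e^(−20(g+h))] − d(1 − R)

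**Worked case, R = 10% and d = 10%.** h = 0.00439 and g = 0.00527. U = 0.9826 × 0.5455 × 0.17565 − 0.10 × 0.90 = 0.09414 − 0.09000 = 0.0041. That is 0.41 percentage points, or 0.21 of a child in 50.

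| True risk R | d = 5% | d = 10% | d = 20% |
|---|---|---|---|
| 5% | 0.10 points | 0.21 | 0.43 |
| 10% | 0.21 | 0.41 | 0.84 |
| 20% | 0.40 | 0.81 | 1.65 |

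Half of each entry is the expected number of uncounted children in 50, so the largest cell is 0.82 of a child.

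**If the SAP extends the on-treatment period.** In the worked case, a lag of 4 weeks after stopping lowers the expected count from 0.21 to 0.13 of a child, and 8 weeks lowers it to about 0.08. That removes roughly one to two thirds of the gap.

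**One missed child in the 9.4 example.** 3/50 is 6% with a 95% interval of 1.3% to 16.5%. At that example's 4% rate, the model puts the chance of even one missed child among 50 at about 4% with 5% stopping and 8% with 10% stopping (U = 0.083 and 0.168 points; 1 − (1 − U)^50). These are upper figures, because the example concerns composite (i), where only stopping for reasons other than a related adverse event matters.

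**Reach of LSFU.** On target dates it ends 336 days after the last injection (6.6.2). Even a child injected only at Week 4b is followed to day 336 from Week 4b. That is past Week 24 (day 140) and Week 48 (day 308), but short of Week 72 (day 476; Appendix II).

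**The case against.** The strongest reply is that nothing here is an error. The protocol names the intercurrent event, chooses a recognised strategy and applies it consistently; the understatement exists only against an estimand that it did not choose. That stands, and it is why the primary estimand should be kept.

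The second reply is that Table 5 leaves other approaches to the SAP, which could also define an on-treatment period running past the last injection. This stands in part. Such a definition would shrink or close the gap. But the Table 5 sentence is optional and concerns missing values, whereas these events are observed.

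The third reply is that nothing goes unreported, and this largely stands. Section 9.6.3 gives outcomes (i) to (iii) after discontinuation with confidence intervals. The worst-grade summaries in 9.6 cover all adverse events, with no on-treatment limit in that sentence. Neither, however, yields a Week 24 proportion. A reader might infer that the events vanish from the reports; the document does not support that.

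A reader might also infer that one missed child would overturn a safety conclusion, because 9.4 says of the 2/50 result "which provides sufficient precision to exclude a rate ≥ 15% based on the upper limit of CI" and the 3/50 interval passes 15%. That sentence is a precision example in a descriptive study. The protocol attaches no decision to 15%, so crossing it changes nothing formally.

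Nor does the point extend to adverse events that began on treatment and worsened later. Section 8.1 has them followed to resolution or stabilisation, and no text freezes the grade at stopping.

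**Conclusion.** The point holds as a low-priority improvement. As written, the Week 24 proportions omit first Grade 3+ events and SAEs that start after an injected child stops and by Week 24, although the protocol itself describes continuing exposure.

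The expected understatement is about 0.1 to 0.8 percentage points at 5-10% true risk and 5-20% stopping, and up to about 1.6 points at 20% risk and 20% stopping. That is less than one child in 50 throughout the range examined. These figures rest on assumed rates, constant hazards and stopping unrelated to risk. If children who stop were at higher risk afterwards, the gap would be larger; if the SAP adds a lag, it would be smaller. The documents do not support calling the primary estimand wrong or the safety conclusions unreliable.

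**What to change.** Keep the while-on-treatment and oral lead-in estimands. Add one row to Table 5 and one sentence to 9.6.1.2 for a supplementary estimate in children who received any injection. It counts outcomes (i) to (iii) from first dose through the planned Week 24 date (day 140 from Week 4b), regardless of discontinuation and using LSFU data. Show the while-on-treatment estimate for the same children beside it.

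If wanted, repeat this at Week 48 (Week 44 in Cohort 2b) with a sentence each in 9.6.2.1 and 9.6.2.2. A Week 72 version is not advised: LSFU reaches that date only for children last injected at Week 24 or later (476 − 336 = 140).

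No new data collection is needed. The downsides should be stated with the estimate:

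- Some events may be due to resumed cART, which restarts within 4 weeks of the last injection on Q4W dosing or at about 8 weeks on Q8W (8.5).
- LSFU visits are sparser, with 16 weeks between LSFU Weeks 8 and 24.
- Children who withdraw from follow-up will be missing.
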